1.0 Background

With the production of high quality imaging systems and improved surgical instruments, video-assisted thoroscopic surgery (VATS) has increased in popularity. When compared to an open technique VATS has been shown to decrease opioid requirements, decrease length of stay and lead to decreased shoulder dysfunction. VATS surgery has also been shown to decrease time until patients resume their normal activity. Despite these statistics, pain following VATS can be severe and long lasting. In addition to non-steroidal anti-inflammatory drugs and systemic opioids, paravertebral nerve blockade and epidural with local anesthetics have emerged as viable adjuncts for control of post-operative pain. Chronic pain after thoracotomy has been studied extensively, and VATS has also been associated with similar rates of chronic pain when compared with open techniques.

Currently, there is no standard of care for post-operative pain control for these patients. The standard of care varies largely, depending on the anesthesiologist or the surgeon. Some anesthesiologists prefer thoracic epidural while others prefer paravertebral block. Each of these pain control techniques have been studied individually and have been shown to provide benefits. Komatsu et al showed that adequate post-thoracotomy pain control was accomplished by continuous paravertebral blockage, while Yoshioka et al showed that epidural analgesia provide effective pain control after surgery. Our study aim is to compare three different methods of pain control that have been proven to show benefit in VATS and compare the efficacy versus the side effects of each techniques. We also aim to look at the effect of these different regional techniques on pain 6 months after surgery.

As mentioned above, several regional techniques have been described for post thoracotomy pain and adapted to VATS. The three most common techniques are:

- 1) paravertebral block using anatomical or ultra-sound guidance
- 2) visual placement of extrapleural paravertebral catheter by thoracic surgeons
- 3) thoracic epidurals

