Previous studies have demonstrated that both thoracic epidurals and paravertebral blocks provide adequate analgesia for VATS. Thoracic epidurals provide excellent pain relief but are associated with hypotension and more nausea/vomiting. Paravertebral catheters have the advantage of having a lower side effect profile than thoracic epidurals. Paravertebral blocks have also been shown to improve respiratory function after surgery. Single shot paravertebral blocks have been described as providing adequate post-VATS pain control, despite a shorter duration of action compared to catheter. In order to evaluate the effectiveness and the side effects of the different pain modalities for post-VATS pain control, we will compare these three different methods of pain blocks:

- 1)single shot paravertebral block
- 2)paravertebral catheters
- 3)thoracic epidural

Rationale and Specific Aims

All of the pain control modalities allow for titration and continuous infusion of local anesthetic to achieve adequate pain control for the duration that the catheter remains in place, except for the single shot paravertebral block. The specific aim of the study is to compare the difference between the three pain blocks in achieving the following:

1. Improved postoperative pain scores
2. Decreased opioid requirements
3. Improved patient satisfaction scores
4. Decreased opioid side effects (Nausea, sedation, ileus, urinary retention, respiratory depression)

The primary endpoint of this study will be VAS pain score. The VAS scores will be taken with both rest and movement.

The secondary endpoint includes intravenous opioid consumption and opioid side effects (nausea, sedation, ileus, urinary retention, respiratory depression). The IV and PO opioid doses will be quantified at 1, 24, 48, and 72 hours. We will also measure postoperative nausea and sedation scores at 1, 24, 48, and 72 hours. We will also measure time to first bowel movement, incidence of urinary retention, incidence of respiratory depression, and time to discharge. If subjects are discharged prior to completing the 72-hour endpoints, efforts will be made to contact them and obtain data points. If unable to be reached, or unable to collect data, we will not consider these deviations since it will not change the integrity of the study data.

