4.0 Study Procedures

All the thoracic epidurals and ultrasound-guided paravertebral blocks will be placed preoperatively. All procedures will be done using sterile technique with masks, hats, and sterile gloves. All procedures will be placed under the supervision of the attending anesthesiologist on the acute pain service or the attending anesthesiologist in the VATS room.

Thoracic epidurals will be placed using the Arrow thoracic epidural kit. Fentanyl and midazolam will be given prior to epidural placement. The epidural will be placed at the appropriate level to cover the entry site for the VATS procedure. Placement will be determined by anatomical landmarks. The epidural needle will be advanced toward the epidural space utilizing a Paramedian approach and loss-of-resistance technique. A sterile catheter will then be secured in place and the epidural infusion will be started at the end of the case.

Ultrasound guided paravertebral catheter and single shot paravertebral block will be accomplished using an ultrasound transducer at the thoracic level. This will be done using an in-plane or out-of-plane approach, at the discretion of the anesthesia staff performing the procedure. Then a needle will be inserted the needle into the paravertebral space and local anesthetic injected. Then a catheter will be placed within the injectate and secured in place in the case of the paravertebral catheter. The 0.2% Ropivacaine will be delivered by OnQ pump.

General anesthesia will be induced and the patient will be placed in the lateral position for the VATS procedure. The patients will be intubated with dual lumen endotracheal tubes and placed on one-lung ventilation for the procedure.

All patients will receive intravenous patient-controlled analgesia (PCA hydromorphone) post-operatively for breakthrough pain. Usual standard of care for pain control following a VATS procedure include scheduling PO acetaminophen and PO oxycodone PRN on POD 1 once patients tolerate diet.

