Patients will be monitored by the primary team during the postoperative period which is after surgery, through hours, 24, 48, and 72. We will also follow up in 6 months with a telephone call to complete a questionnaire which will conclude all study participation. The potential complications or risks associated with all three procedures are risks that are normally expected and we will not consider these adverse events. Any post-operative complication that is associated with the required medication per study protocol such as drug toxicity or nausea and vomiting related to taking the scheduled Tylenol and PRN (as needed) oxycodone for pain will be reported as an adverse event. This required drug regimen is specific to the study. All of these events will be reported to the Principal investigator and will be addressed immediately. These adverse events will be assessed to determine if they meet prompt reporting criteria, and if so, we will report these events to the IRB committee using the prompt reporting form. Events not promptly reportable will be reported to the IRB at the time of study renewal, if applicable."

Normal post-operative adverse events such as nausea, vomiting, and pruritus will not be considered a recordable or reportable event to the IRB since it's part of the post-operative course expected with these procedures.

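### The listed opioid side effects can be compared by arm, but hypotension, vomiting, pruritus and block complications have no planned collection, so the aim of comparing each technique's side effects is only partly answerable

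*Combined protocol and SAP*

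**What the plan says.** Section 1.0 gives the aim as to "compare the efficacy versus the side effects of each techniques". It also states the trade-off it expects: "Thoracic epidurals provide excellent pain relief but are associated with hypotension and more nausea/vomiting", while paravertebral catheters are credited with fewer side effects. The specific aims in the same section are narrower. Their side-effect item reads "Decreased opioid side effects (Nausea, sedation, ileus, urinary retention, respiratory depression" (closing bracket omitted).

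Sections 4.0 and 7.0 provide for nausea and sedation scores, each from 0 to 3, at 1, 24, 48 and 72 hours, with Mantel-Haenszel chi-square tests between groups at each time. Section 7.0 adds time to first bowel movement and the incidence of urinary retention and of respiratory depression. Section 4.0 adds length of stay and readmission.

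Section 5.0 then sets three rules:

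- For the blocks: "The potential complications or risks associated with all three procedures are risks that are normally expected and we will not consider these adverse events".
- For the oral analgesics: "nausea and vomiting related to taking the scheduled Tylenol and PRN (as needed) oxycodone for pain will be reported as an adverse event". The reason given is that this regimen is particular to the study.
- For the ordinary postoperative course: "Normal post-operative adverse events such as nausea, vomiting, and pruritus will not be considered a recordable or reportable event". The sentence continues by naming the IRB.

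Section 4.0 describes the same oral regimen differently: "Usual standard of care for pain control following a VATS procedure include scheduling PO acetaminophen and PO oxycodone PRN".

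**The concern.** The three blocks are the randomized interventions, so their complications are part of what the trial compares. Adverse-event recording would normally be the fallback for a harm that is not a named outcome. Here Section 5.0 takes block complications out of the adverse-event definition in every arm, with no exception for severity. It also sets aside vomiting and pruritus that are judged part of the normal course.

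An analgesic benefit for one technique could then be reported without some of the harms that the Background itself associates with it, hypotension above all. Later recovery of the data may not be possible, because Sections 8.0 and 9.0 provide for destroying patient identifiers at the end of the study.

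A second problem is attribution. Nausea or vomiting is an adverse event if it is due to acetaminophen or oxycodone, and not if it is normal. Every patient also has hydromorphone PCA, the epidural arm additionally receives epidural hydromorphone, and no blinding is described.

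**Working it through.** The plan states no figure on this point. The check traces each harm from the aims through collection to the adverse-event rules.

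| Harm | Named in Section 1.0 | Collected as an outcome | Treatment in Section 5.0 |
|---|---|---|---|
| Nausea | Yes | Yes, 0–3 score at four times | Split by presumed cause |
| Sedation | Yes | Yes, 0–3 score at four times | Not mentioned |
| Ileus | Yes | Yes, through time to first bowel movement | Not mentioned |
| Urinary retention | Yes | Yes, incidence | Not mentioned |
| Respiratory depression | Yes | Yes, incidence | Not mentioned |
| Vomiting | Yes, for the epidural | No | Split by presumed cause |
| Hypotension | Yes, for the epidural | No | Not mentioned; outside the definition if a block complication |
| Pruritus | No | No | Set aside if normal |
| Block or catheter complications | Only as side effects of the techniques in general | No | Not adverse events |

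**Step 1: the specific aim.** All 5 of the 5 listed opioid side effects are collected, whatever their cause.

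**Step 2: the broader aim.** The last four rows have no planned collection as outcomes. The only route left is Section 5.0, and it admits only complications attributed to the required medication. Section 7.0 promises summaries of all data by group, so the gap is in collection first.

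**Step 3: the attribution rule.** The two nausea and vomiting rules divide events by cause, but no criterion is given for deciding the cause. A patient on PCA hydromorphone who takes oxycodone and vomits could be placed under either rule. The distinction also rests on a regimen that Section 4.0 presents as usual care and Section 5.0 as study-specific.

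**Step 4: what 40 per arm could show if the harms were recorded.** Input: n = 40 per group (Section 3.0).

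- No events in one arm: the exact two-sided 95% upper limit is 1 − 0.025^(1/n) = 1 − 0.025^(1/40) = 0.088, or 8.8%.
- Two arms: power = Φ{[|p1 − p2| − 1.96·√(2p̄(1 − p̄)/n)] / √[(p1(1 − p1) + p2(1 − p2))/n]}, where p̄ is the mean of p1 and p2. The documents give no event rates, so those below are assumptions.
  - 30% vs 10%: (0.20 − 1.96 × 0.0894)/0.0866 = 0.285, power about 61%.
  - 40% vs 10%: about 89%.
  - 40% vs 20%: about 50%.
  - 20% vs 10%: about 24%.
- At 30% vs 10%, the approximate 95% interval for the difference is 20 ± 1.96 × 8.66 = 20 ± 17 percentage points.

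**The case against.** The strongest reply is that Section 5.0 concerns reporting, not data collection. The sentence on nausea, vomiting and pruritus ends by referring to the IRB. A reader who stops before those words might infer a ban on recording, and the text does not support that. Nor does it call block complications unrecordable; it says only that they do not count as adverse events. This stands. It does not close the gap, because no other section provides for collecting these harms.

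A reader might also infer that the trial cannot answer its side-effect question at all. The documents do not support this either. The specific aim lists five opioid side effects, all five are collected, and nausea and sedation have a named test. Only the wider aim in Section 1.0 is left partly unanswered.

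Two further stronger readings fail. The nausea and vomiting rules do not strictly contradict each other, since they separate events by cause; the difficulty is applying them. And unreliable attribution does not bias the nausea outcome, which is scored 0–3 regardless of cause. It affects adverse-event listings only.

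Finally, the hypotheses in Section 7.0 set the epidural and the paravertebral catheter against the single-shot block, not against each other. That is correct, but harms of the techniques bear on those contrasts too. It is also fair that 40 per arm gives limited precision. That is a reason to report intervals, not a reason to leave the harms unrecorded.

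**Conclusion.** The concern holds in a limited form. The five listed opioid side effects can be compared by arm. The wider comparison of each technique's side effects can be made only in part, because hypotension, vomiting, pruritus and block or catheter complications have no planned collection and Section 5.0 removes the usual fallback for most of them. Information on these harms is not strictly zero, since events attributed to the required medication would be reported, but those reports would rest on a causal judgment with no stated criterion.

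Hypotension is the clearest omission, because the protocol itself names it as a drawback of the epidural. The primary outcome, its analysis and the listed secondary outcomes are untouched, so this is an inexpensive improvement rather than a flaw that undermines the trial.

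The conclusion assumes that the case form follows the outcome lists in the protocol. If it already has fields for these harms, only the wording of Section 5.0, the planned table and the conflict over the oral regimen remain to be settled.

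**What to change.** 1. State in Section 5.0 that the rule on expected events decides only what goes to the IRB, and does not limit what is recorded.
2. Record hypotension, vomiting, pruritus, block failure and block or catheter complications on the case form for all patients in all three arms, whatever the presumed cause, with definitions and time points set in advance.
3. Add to Section 7.0 a safety table of these events by randomized arm with confidence intervals, and note that 40 per arm gives limited precision.
4. Reconcile Sections 4.0 and 5.0 on whether the acetaminophen/oxycodone regimen is usual care or specific to the study. If adverse-event listings are still to be split by cause, state how cause is judged.

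The cost is a few chart-based REDCap fields, slightly more data entry and one extra table. Treatment, visits and sample size do not change.

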6.0 Study Withdrawal/Discontinuation

The patient can withdraw from the study at any time by contacting the research team or acute pain anesthesia resident. In such an event, the catheter will be removed immediately, provided no anticoagulants had been administered. Patient may still have access to Alaris pump and will have access to all the IV and oral pain medications. Anesthesia acute pain team will continue to follow the patient for 24 hours. 24 hours after catheter removal, anesthesia acute pain team will sign off and all further pain management will be done by the primary team.

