3.0 Enrollment/Randomization

All VATS cases scheduled by thoracic surgeons at IU Health University Hospital will be identified. The subjects will be contacted face-to-face prior to surgery. They will be informed about the study and all questions will be answered. The potential subjects will be given a copy of the informed consent form and authorization form. The subjects will then be contacted face-to-face in POCU on the day of surgery and if participation is agreed, written consent will be taken.

A total of 120 subjects will be randomized by a computer program into three groups (40 per group):

1. US- Guided Paravertebral Catheter (PVB-A)- The Alaris pump will deliver 0.2% Ropivacaine at a rate of 10 ml/hr
2. Single Shot Paravertebral Block- placed by ultrasound using 0.2% Ropivacaine bolus.
3. Thoracic Epidural- The Alaris pump will deliver an epidural mixture of 0.125% bupiv/hydromorphone

Randomization will be stratified by prior opioid experience (opioid naïve or opioid tolerant). Separate randomization lists will be used for the two strata.

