Opioid usage at 1,24,48,72 hours after the block will be recorded by a member of the research team. Pain scores at rest and on movement (knee flexion) will be measured by the investigator using Visual Analog Scale (VAS). Nausea will be measured using a categorical scoring system (none=0; mild=1; moderate=2; severe=3). Sedation scores will also be assessed by a member of the study team using a sedation scale (awake and alert=0; quietly awake=1; asleep but easily roused=2; deep sleep=3). All these parameters will be measured at 1, 24, 48 and 72 hours after the epidural or PVB. Patients will be encouraged to ambulate on postoperative day 1 under supervision.

All catheters will be removed by APS (Acute Pain Service) while patients are still in the hospital. APS will continue to follow the patients until catheter removal. Patient's hospital length of stay and readmission rate will be recorded from NSQIP (National Surgical Quality Improvement Program) data.

All patients will receive a phone call 6 months after surgery for assessment for chronic post-surgical pain. Patients will be assessed by a member of the research team over the phone. They will be assessed on their pain score and narcotic usage by using the Brief Pain Inventory. Study participation will conclude after the 6 month follow questionnaire has been completed.

5.0 Reporting of Adverse Events or Unanticipated Problems involving Risk to Participants or Others

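### Section 6.0 makes leaving the study an automatic trigger for catheter removal, so a patient who only wants to stop assessments would lose a working block

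*Combined protocol and SAP*

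**What the plan says.** Section 6.0 opens with the right to leave: "The patient can withdraw from the study at any time by contacting the research team or acute pain anesthesia resident". The consequence follows directly: "In such an event, the catheter will be removed immediately, provided no anticoagulants had been administered". The wording is mandatory and immediate, and it carries one condition. The section then describes what the patient keeps: "Patient may still have access to Alaris pump and will have access to all the IV and oral pain medications". The acute pain team follows the patient until 24 hours after the catheter comes out and then hands over to the primary team.

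Other sections bear on this:

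- Section 1.0, on usual practice: "Some anesthesiologists prefer thoracic epidural while others prefer paravertebral block".
- Rationale and Specific Aims, on what the catheter techniques offer: "adequate pain control for the duration that the catheter remains in place, except for the single shot paravertebral block".
- Section 2.0 makes wanting a regional technique for pain after surgery an inclusion criterion.
- Section 3.0 plans three arms of 40. Two of them, paravertebral catheter and thoracic epidural, use an indwelling catheter.
- Section 4.0, on background analgesia in every arm: "All patients will receive intravenous patient-controlled analgesia (PCA hydromorphone) post-operatively for breakthrough pain". On catheter care: "APS will continue to follow the patients until catheter removal". It also has all catheters taken out before the patient leaves hospital.

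**The concern.** Leaving a study can mean two different things. A patient may be tired of repeated pain, nausea and sedation scoring, or may want the block itself stopped. Section 6.0 treats these as one event and attaches the same action to both. Nothing elsewhere in the document separates them: the remarks in Section 1.0 on incomplete data concern only the 72-hour and 6-month collections, and Section 4.0 covers only routine removal.

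At stake is the care of a patient whose block is working. If the rule is followed as written, the block ends because research participation ended, not because the patient or the pain service judged that it should. A patient who understands this may also feel that leaving has a price.

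**Working it through.** The plan gives no figure for this rule, so there is none to reproduce. The check sets the provisions side by side and then bounds the reach.

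**Step 1. What the rule does for each kind of request** (patient with a catheter in place, no anticoagulant given)

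- Stop the block only, stay in the study: Section 6.0 does not address this; it deals only with leaving the study.
- Stop both the block and the assessments: the catheter comes out, as the patient wishes.
- Stop the assessments only: the catheter still comes out. The patient did not ask for this, and no clinical judgement is called for.

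The third case is the problem.

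**Step 2. Whether the block is purely a research intervention**

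Section 2.0 admits only patients who want regional anesthesia for themselves. Section 1.0 presents epidural and paravertebral block as alternatives that clinicians already choose between. Support is clearest for the epidural arm. For the other catheter arm it is partly inference: the list of common techniques in Section 1.0 names image- or landmark-guided paravertebral block and a surgeon-placed extrapleural catheter, but not expressly the ultrasound-guided continuous catheter used here.

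**Step 3. Whether removal costs the patient something**

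By the protocol's own rationale, the catheter techniques can be titrated and continued while the catheter is in, and the single injection cannot. Removal ends that advantage.

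**Step 4. Whether the sentence on the Alaris pump rescues the block**

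Section 3.0 names that pump for both catheter infusions, although Section 4.0 names an OnQ pump for the paravertebral ropivacaine. In Section 6.0 the Alaris sentence comes after the removal instruction and is only permissive. It may refer to intravenous patient-controlled analgesia, or to patients whose catheter stays because of anticoagulants. It does not say that the block continues.

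**Step 5. Reach** (arm sizes from Section 3.0)

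- Patients planned to have a catheter: 2 × 40 = 80.
- Share of the trial: 80 / 120 = 66.7%.
- Epidural arm alone, where support from usual practice is clearest: 40 / 120 = 33.3%.
- Single-shot arm: 0 of 40, since there is no catheter to remove.

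These are ceilings on who could be exposed, not estimates of who will be. Exposure lasts only while the catheter is in, which ends before discharge. The document states no expected withdrawal rate, so no count of affected patients follows.

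**The case against.** The strongest reply is that stopping a protocol-assigned infusion when consent ends is a defensible default. Withdrawal is the patient's own act, one of the two named contacts is a clinician on the pain service, and nothing says that a catheter would be pulled over the patient's objection. Intravenous and oral drugs stay available and the pain team remains involved for a day afterwards. In practice, a sensible resident might ask what the patient wants.

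Much of this stands, and it limits the harm: the patient is not left without pain relief. It does not remove the point, because the text tells staff to remove the catheter and gives them no alternative to offer. A need for supervision does not justify the rule either. The acute pain service already follows patients until removal, and the anticoagulant exception already leaves some withdrawn patients with a catheter for a time.

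A second reply is that the consent form may offer these choices. It may; the consent pages were not in the text reviewed. Section 6.0 would then need to be brought into line with it. For the same reason, silence in Section 6.0 on keeping or collecting data after withdrawal is not counted here as a gap in the plan.

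**Conclusion.** The point holds as a minor matter of patient care. Section 6.0 states a rule that, followed literally, ends a working block for a patient who asked only to stop being assessed. It can reach at most 80 of 120 patients, for the in-hospital period with a catheter. The conclusion assumes that staff apply the section as written and that the consent pages do not override it.

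A reader might infer more: that because the rule touches only the catheter arms, it produces unequal missing data and so biases the comparison of pain scores at 24 and 48 hours (the primary outcome in Section 7.0). The documents do not support that. Scores are lost because a patient withdraws and is no longer assessed, not because a catheter is removed. Each arm plans 40 × 2 = 80 primary scores per VAS condition. If nothing is collected afterwards, one withdrawal before 24 hours costs 2 / 80 = 2.5% of them, in the single-shot arm exactly as in a catheter arm. In that case removal cannot alter any later score, and if scores are collected, that loss does not arise. With no withdrawal rates by arm, nothing can be said about bias or power, and no such claim is made.

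**What to change.** Amend Section 6.0 so that withdrawal from study assessments does not by itself trigger catheter removal. In substance:

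- At withdrawal, ask the patient whether they want to stop the assessments, the block, or both, and record the answer.
- If the patient does not ask for the block to stop, removal is decided by the acute pain service and the patient on clinical grounds.
- Keep the anticoagulant safeguard for any removal, and keep acute pain service follow-up until 24 hours after the catheter is out.

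The cost is one short protocol amendment, one field on a form, and matching consent wording if the consent pages do not already offer the choice. Sample size, randomization and the primary model are unchanged. The small downside is that the acute pain service follows a withdrawn patient for as long as the catheter stays in, which Section 4.0 already provides for.
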